### **10.6 Efficacy Subgroup Analysis**

Subgroup analyses will be performed for the primary efficacy endpoint of SVR12.

Within each subgroup, the number and percentage of subjects achieving SVR12 will be calculated for the ITT population. The 2-sided 95% Wilson score CI will be produced if there are at least 10 subjects in the subgroup.

The following subgroups will be analyzed:

- HCV genotype (1, 2, 3, 4, 5, or 6) and available subtype (based on the latest determination of genotype from the baseline sample [by the central laboratory or by phylogenetic analysis, with preference given to the phylogenetic analysis results] at the time of the primary SVR12 analysis);

- Prior HCV treatment history (treatment-naïve or treatment-experienced);
- For treatment-experienced subjects, type of prior treatment experience (IFN- or SOF-based);
- For treatment experienced subjects, type of non-response to previous treatment (on-treatment non-responder or breakthrough, post-treatment relapse, or unknown/other);
- Screening HIV co-infection status (HCV mono-infected or HCV/HIV co-infected);
- IL28B genotype (CC or non-CC);
- Sex (male or female);
- Age (< 65 or ≥ 65 years) and (< 75 or ≥ 75 years);
- Geographic region (China or South Korea);
- Type of Asian descent (Chinese or Korean);
- Baseline BMI (< 30 or ≥ 30 kg/m^2);
- Baseline HCV RNA level (< 1,000,000 or ≥ 1,000,000 IU/mL; < 6,000,000 or ≥ 6,000,000 IU/mL; < 10,000,000 or ≥ 10,000,000 IU/mL);
- Baseline HOMA-IR (< 2 or ≥ 2 mU × mmol/L);
- Baseline platelet count (< 100 or ≥ 100 × 10^9/L);
- Baseline albumin (< 35 or ≥ 35 g/L);
- Baseline alpha fetoprotein (< 20 or ≥ 20 ng/mL);
- Baseline Child-Pugh score (5, 6, or > 6);
- Baseline creatinine clearance (< 60, ≥ 60 to < 90, or ≥ 90 mL/min);
- Baseline eGFR by C-MDRD (< 60, ≥ 60 to < 90, or ≥ 90 mL/min/1.73 m^2);
- History of diabetes (yes/no);
- History of bleeding disorders (yes/no);
- History of depression or bipolar disorder (yes/no);
- History of cardiovascular disease (yes/no);
- Baseline metabolic syndrome (yes/no);
- Injection drug use (yes, within last 12 months; yes, more than 12 months ago; or no);

- Baseline stable opiate substitution use (yes/no);
- Baseline hepato-protectant medication use (yes/no);
- Study drug compliance (yes/no);
- Concomitant use of PPIs (yes/no).

The summaries described above will be performed for the set of all subjects and for the geographic region of China.

A logistic regression model will be used to explore the associations between each of the subgroup variables and SVR12 by fitting a logistic regression model on all subjects in the mITT-GT-VF population. Among all candidate predictors, continuous measurements will be used where possible (e.g., continuous baseline log10 HCV RNA level, continuous age, continuous BMI) in the logistic regression model. A stepwise logistic regression approach will be used to assess the strength of each subgroup variable in predicting SVR12, with a significance level of 0.10 to enter and remain in the model.

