## 4.2 Design Diagram

This is a Phase 3, single-arm, open-label, multicenter study to evaluate the efficacy, safety and pharmacokinetics of ABT-493/ABT-530 in chronic HCV GT1 to GT6-infected Asian adult subjects with compensated cirrhosis with or without HIV co-infection who are HCV treatment-naïve or treatment-experienced with IFN (alpha, beta or pegIFN) with or without RBV OR sofosbuvir with RBV with or without IFN. This study consists of a Treatment Period and a Post-Treatment (PT) Period. The study schematic is presented in [Figure 1](#).

The study is designed to enroll approximately 160 subjects to meet scientific and regulatory objectives without enrolling an undue number of subjects in alignment with scientific and ethical considerations. From China, a minimum of 60 GT1-infected subjects, a minimum of 36 GT2-infected subjects and approximately 24 GT3, 4, 5 or 6-infected subjects will be enrolled into this study. From the regional Asian country of South Korea, approximately 30 GT1-infected subjects and approximately 10 GT2-infected subjects will also be enrolled into this study. Of the approximately 160 subjects, a maximum of 16 HCV/HIV co-infected subjects will be enrolled.

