### **4.3 Sample Size**

It is planned to enroll approximately 160 subjects. The sample size for this study is driven by the expected sample size requirements for each genotype and geographical region for this secondary indication. No formal hypothesis is being tested in this study. If the observed SVR12 rate in this study is 95% among 160 subjects, then the two-sided 95% confidence interval (CI) calculated using the normal approximation for a single binomial proportion is 91.6% to 98.4%.

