**Analysis will be performed separately for each HCV subtype and treatment duration within each listing**

**Analysis 1:** The following analyses will be performed for subjects who enroll in South Korea:

- A listing of all baseline polymorphisms ( $\geq 2\%$  detection threshold) at signature amino acid positions for each DAA target (NS3 and NS5A) (ITT population).
- The number and percentage of subjects with baseline polymorphisms at detection-thresholds of  $\geq 2\%$  and  $\geq 15\%$  at signature amino acid positions (ITT population). This table includes prevalence of each baseline polymorphism, and a summary of number of subjects with polymorphisms in NS3 only, in NS5A only, any in NS3, any in NS5A, any in NS3 or NS5A, any in NS3 and NS5A.
- Total number and percentage of subjects with baseline polymorphisms *at the key subset of amino acid positions* in NS3 only, in NS5A only, any in NS3, any in NS5A, any in NS3 or NS5A, any in NS3 and NS5A (ITT population) by genotype, subtype, and total.

**Analysis 2:** The impact of baseline polymorphisms on treatment outcome will be assessed for **mITT-GT-VF** population for subjects who enroll in South Korea as follows: for each polymorphism, the SVR12 rate will be calculated for subjects with and without the polymorphism and the 2 rates will be compared using Fisher's exact test. Analysis will be grouped by HCV subtype, treatment duration, and DAA target (NS3 or NS5A). The following will be included in the analyses of impact of baseline polymorphisms on treatment outcome:

- Polymorphisms at signature amino acid positions (vs. no polymorphisms at that position), using detection thresholds of both  $\geq 2\%$  and  $\geq 15\%$ . The analysis will include the number of subjects with polymorphisms in NS3 only, in NS5A only, any in NS3, any in NS5A, any in NS3 or NS5A, any in NS3 + NS5A.

- Each polymorphism at signature amino acid position (vs not that polymorphism) using detection thresholds of  $\geq 2\%$  and  $\geq 15\%$ . The analysis will include the number of subjects with polymorphisms in NS3 only, in NS5A only, any in NS3, any in NS5A, any in NS3 or NS5A, any in NS3 + NS5A.

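### SAP 10.6 plans a stepwise logistic regression over 29 candidate factors with about 1 to 2 virologic failures expected, and sets no minimum number of failures

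*SAP*

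**What the plan says.** SAP 10.6 lists 29 subgroup factors for SVR12 and then adds a model: "A stepwise logistic regression approach will be used to assess the strength of each subgroup variable in predicting" SVR12, with a level of 0.10 both to enter and to remain. All the subgroup variables are candidates, in continuous form where possible. The model is specified as "fitting a logistic regression model on all subjects in the mITT-GT-VF population". SAP 5.1.2 defines that population by removing every subject who missed SVR12 for a reason other than on-treatment virologic failure or relapse, so virologic failures are the only events.

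SAP 10.6 withholds a subgroup confidence interval when there are fewer than 10 subjects. It sets no corresponding minimum number of failures for the regression, no limit on candidates, and no rule for separation or for zero failures. Two candidates apply to treatment-experienced subjects only, one of them being "For treatment-experienced subjects, type of prior treatment experience (IFN- or SOF-based"), and their coding for treatment-naive subjects is not stated. SAP 10.6 describes the model as exploratory, and SAP 10.2 says that no hypothesis is tested on the primary or secondary endpoints.

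**The concern.** A logistic model draws its information from the rarer outcome, here the virologic failures. If only one or two occur, a search over 29 candidates at 0.10 has almost nothing to work with. A factor that separates the failures from the responders has no finite odds ratio, and a factor that is kept may be there by chance. SAP 4.4 sends the primary-analysis results into the clinical study report and a marketing submission. A factor such as genotype, platelet count or proton pump inhibitor use could then appear as associated with response on the strength of one or two subjects.

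**Working it through.** **1. The plan's own figure.** SAP 4.3: "It is planned to enroll approximately 160 subjects". At 95% SVR12 the interval "calculated using the normal approximation for a single binomial proportion is 91.6% to 98.4"%. Check: 0.95 ± 1.96 × √(0.95 × 0.05 / 160) = 0.95 ± 0.0338, or 91.6% to 98.4%. It reproduces. It implies 160 × 0.05 = 8 non-responders for any reason. Neither document states an expected number of virologic failures, so it has to be derived.

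**2. Planned mix (SAP 4.2).** China: "a minimum of 60 GT1-infected subjects, a minimum of 36 GT2-infected subjects and approximately 24 GT3, 4, 5 or 6-infected subjects". South Korea: "approximately 30 GT1-infected subjects and approximately 10 GT2-infected subjects". Total: 90 GT1, 46 GT2 and 24 GT3 to GT6, which is 160.

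**3. Virologic failures in earlier cirrhotic subjects (protocol 5.6.1, Tables 6 and 8).**

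| Group | On-treatment failure | Relapse |
|---|---|---|
| GT1 | 0/101 | 1/98 |
| GT2 | 0/35 | 0/35 |
| GT4, GT5, GT6 | 0/20, 0/2, 0/7 | 0/19, 0/2, 0/7 |
| GT3 naive | 0/65 | 0/64 |
| GT3 experienced | 1/51 | 2/50 |

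**4. Expected failures.** Let k be the number of treatment-experienced GT3 subjects among the 24. The plan does not fix k. Expected = 90 × 1/101 + 46 × 0 + k × 3/51.
- k = 0: 0.9
- k = 12: 0.89 + 0.71 = 1.6
- k = 24: 0.89 + 1.41 = 2.3

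Pooled: 4 failures in 101 + 35 + 20 + 2 + 7 + 65 + 51 = 281 subjects, or 1.42%. That gives 2.3 of 160, with Clopper-Pearson limits of 0.6 to 5.8.

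**5. Events per candidate.** From 0.9/29 = 0.03 to 2.3/29 = 0.08. If all 8 non-responders in step 1 were virologic failures, 8/29 = 0.28. The number of parameters exceeds 29, because several factors have more than two levels.

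**6. Poisson probabilities.**

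| Mean | No failures | 2 or fewer |
|---|---|---|
| 0.9 | 41% | 94% |
| 1.5 | 22% | 81% |
| 2.3 | 10% | 60% |

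**7. Stepwise search on pure noise.** As a rough guide, the chance that at least one of 29 independent null candidates passes 0.10 is 1 − 0.9^29 = 95%. The simulation used 157 subjects, 29 candidates without effect, a score test to enter and a Wald test on the variable just entered to stay (both at 0.10), a linear-programming check for separation, and 500 runs per event count. The covariate distributions are assumed.

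| Failures | A noise variable enters | Separation | Noise kept | Separation or noise kept |
|---|---|---|---|---|
| 1 | 94% | 78% | 1% | 79% |
| 2 | 88% | 51% | 31% | 81% |
| 3 | 92% | 42% | 43% | 85% |
| 8 | 93% | 30% | 57% | 88% |

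The remaining runs mostly end with an empty model. With only 15 common candidates, the last column falls to 49% at one failure and 64% at two.

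**The case against.** The strongest reply is that the model only explores associations. It leaves the primary SVR12 estimate and its interval alone, so little harm follows. That stands, and it limits the weight of the point. Several stronger readings are tempting, and the documents do not support them.

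- **That the search will almost certainly select noise or fail by separation.** Zero failures is a real possibility, and then nothing is selected. Allowing for it, the chance of separation or retained noise is roughly (1 − 0.41) × 0.80 = 47% at a mean of 0.9 and (1 − 0.10) × 0.83 = 75% at 2.3. Entry rates near 95% also ignore the stay step, which the SAP requires.
- **That any selected factor must be chance.** Treatment-experienced GT3 subjects with cirrhosis had 3 failures in 51, against none in 35 with GT2, so a real effect is plausible. One or two events cannot show it reliably.
- **That every treatment-naive subject would drop out.** The SAP fits the model to all of mITT-GT-VF and does not say how the two factors for experienced subjects are coded. A naive level is as possible as complete-case deletion. This is a gap in coding, not a stated exclusion.
- **That the South Korean resistance comparisons fail in the same way.** In SAP 10.8, Analysis 2, "the 2 rates will be compared using Fisher's exact test". That test remains valid with sparse data and involves no stepwise search. It would have little power, which is a different matter.

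It can also be said that SAP 10.4 and 10.8 already plan listings of non-responders and of virologic failures. They do, but those listings are not specified to show the subgroup variables, and nothing stops the model being run.

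**Conclusion.** The point holds as a correctable weakness in an exploratory analysis. On the protocol's own data the regression would have about 1 to 2 events for 29 candidates, and each likely outcome is uninformative: no fit, separation, a factor kept on one or two subjects, or an empty model. The expected count rests on two assumptions: that earlier cirrhotic failure rates carry over, and that enrolment follows the planned mix with the number of treatment-experienced GT3 subjects unknown. Even the upper limit of 5.8 failures gives only 5.8/29 = 0.20 per candidate. The figure of about 80% also depends on the assumed covariates and falls with fewer candidates. It should not be read as a statement about the primary result, which is unaffected.

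**What to change.** Add to SAP 10.6:

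- If mITT-GT-VF contains fewer than 10 virologic failures, fit no regression. Give a by-subject listing of the failures with their subgroup variables, beside the planned subgroup rates and Wilson intervals.
- If it contains 10 or more, replace the stepwise search with Firth-penalised logistic models, one pre-named factor at a time (for example genotype, prior treatment history, baseline log10 HCV RNA, platelet count).
- Code the two prior-treatment factors with a treatment-naive level, and use only one of geographic region and Asian descent.

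The floor of 10 is a judgement. It uses the same number as the SAP's floor for subgroup intervals, though it counts failures and not subjects. Since even the upper limit of 5.8 lies below it, the listing will very probably replace the model. The cost is a paragraph of SAP text and the loss of an exploratory multivariable model at low event counts; programming should fall.

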## **10.7 Additional Efficacy Analyses**

The ITT population will be used to summarize the following additional efficacy endpoints for the set of all subjects and for the geographic region of China:

- The percentage of subjects with HCV RNA < LLOQ at each post-baseline visit in the Treatment Period (using data as observed);
- The percentage of subjects with SVR4;
- A summary of reasons for SVR4 non-response (e.g., on-treatment virologic failure, relapse, re-infection, other);
- The percentage of subjects with HCV virologic failure through PT Week 12 (i.e., the SVR12 non-responders due to on-treatment virologic failure or Relapse12);
- The percentage of subjects with SVR24\*;
- A summary of reasons for SVR24 non-response (e.g., on-treatment virologic failure, relapse, re-infection, other)\*;

- The percentage of subjects who relapsed after achieving SVR12 (**Relapse24**).

\* These endpoints will be summarized for the HCV/HIV co-infected subjects (determined at Screening) within the populations/groups identified above.

In the above analyses for SVR, HCV virologic failure, and relapse, the number and percentage of subjects along with a two-sided 95% Wilson score CI will be calculated. Imputations for missing data will be performed as described in Section 6.3 for analysis of SVR, HCV virologic failure, and relapse. All other endpoints will be presented using data as observed.

As additional endpoints, the secondary endpoints will be summarized for the geographic region of China. A summary of the subjects who completed treatment and relapsed (defined as **Relapseoverall**) will be prepared displaying the number of subjects relapsing overall and by SVR visit window (within the SVR4, SVR12, SVR24 windows or after SVR24 window), including the subject number and the SVR visit window corresponding to the first HCV RNA value of those indicating the occurrence of relapse. A similar listing will be prepared for subjects who prematurely discontinued treatment and relapsed after having HCV RNA < LLOQ at their Final Treatment Visit. These summaries will be performed for the overall ITT population and for the geographic region of China within the ITT population.

Listings of subject numbers with reason for non-response will be prepared for the SVR endpoints.

The concordance between SVR12 and SVR24 will be assessed by the agreement between SVR12 and SVR24 and the positive predictive value (PPV) and negative predictive value (NPV) of SVR12 on SVR24. The agreement between SVR12 and SVR24 is a percentage defined as the number of subjects achieving both SVR12 and SVR24 and the number of subjects where both SVR12 and SVR24 are not achieved. The PPV of SVR12 on SVR24 is the proportion of subjects who achieve SVR24 out of all subjects who achieved SVR12. The NPV of SVR12 on SVR24 is the proportion of subjects who do not achieve SVR24 out of all subjects who did not achieve SVR12. Similarly, the concordance between SVR4 and

SVR12 will be summarized. These summaries will be performed for the overall ITT population and for the geographic region of China within the ITT population.

For each additional analysis, if applicable, a two-sided 95% CI will be produced only if there are at least 10 subjects in the summary.

## **10.8 Resistance Analyses**

For subjects who enroll in South Korea, full length NS3/4A and NS5A from baseline samples will be sequenced by next generation sequencing (NGS). For subjects who enroll in South Korea who experience HCV virologic failure (on-treatment HCV virologic failure or post-treatment relapse as defined in Section 10.1), full length NS3/4A and NS5A genes from the first sample after virologic failure with HCV RNA  $\geq$  1000 IU/mL will be sequenced by next generation sequencing (NGS). For genotype 1-infected subjects experiencing virologic failure who enroll in China, amino acids 1 – 181 in NS3 and 1 – 215 in NS5A from the baseline sample and the first sample after virologic failure with HCV RNA  $\geq$  1000 IU/mL will be sequenced by population sequencing. An appropriate subtype-specific prototypic reference sequence will be used for comparison with sequences from samples. Subjects who experience HCV virologic failure will be referred to as subjects in the primary virologic failure (PVF) population, and a listing by subject that includes HCV subtype, IL28B genotype, reason for SVR12 non-response, time point(s) sequenced as closest to time of HCV virologic failure, and HCV RNA value at the HCV virologic failure time point(s) will be produced for these subjects. In addition, all listings described below will display HCV subtype and reason for SVR12 non-response in the subject identifier for each subject. A separate listing will delineate all subjects in the PVF population for whom no sequencing was performed (e.g., lost to follow-up while HCV RNA  $\leq$  1000 IU/mL).

Subjects from South Korea and GT1-infected subjects from China treated with active study drug who do not achieve SVR12 and who do not meet the above criteria for the PVF population (i.e., prematurely discontinue study drug with no on-treatment HCV virologic failure, have HCV reinfection, are missing SVR12 data or have other reasons as described

in Section 10.1, Reasons for SVR12 Non-Response), but have a time point with HCV RNA  $\geq 1000$  IU/mL after treatment discontinuation, will have the sample at that time point sequenced. For subjects who are lost to follow-up with less than 6 weeks of therapy while not virally suppressed (e.g., HCV RNA never  $<$  LLOQ or have increase in viral load post-nadir), the sample at the latest available time point with HCV RNA  $\geq 1000$  IU/mL and the corresponding baseline sample will be sequenced. These subjects will be referred to as the non-PVF population. A listing of all subjects in the non-PVF population with post-baseline sequencing available will be created that is similar to the listing of subjects in the PVF population with post-baseline sequencing. For each DAA target, signature amino acid positions and a key subset of amino acid positions are shown in Table 10. Appropriate subtype-specific prototypic reference sequences will be used for comparison with sequences from samples.

**Table 10. List of Signature Amino Acid Positions and a Key Subset of Amino Acid Positions**

Target	Signature Amino Acid Positions	Key Subset of Amino Acid Positions
GT1, NS3	36, 43 (GT1a only), 54, 55, 56, 80, 107, 122, 132 (GT1a only), 155, 156, 158, 168, 170, 175 (GT1b only)	155, 156, 168
GT1, NS5A	24, 28, 29, 30, 31, 32, 54 (GT1b only), 58, 62, 92, 93	24, 28, 30, 31, 58, 92, 93
GT2, 4, 5, 6, NS3	36, 43, 54, 55, 56, 80, 155, 156, 168	155, 156, 168
GT2, 4, 5, 6, NS5A	24, 28, 29, 30, 31, 32, 58, 62, 92, 93	24, 28, 30, 31, 58, 92, 93
GT3, NS3	36, 43, 54, 55, 56, 80, 155, 156, 166, 168	155, 156, 168
GT3, NS5A	24, 28, 29, 30, 31, 32, 58, 92, and 93	24, 28, 30, 31, 58, 92, 93

Only samples with an HCV RNA level of  $\geq 1000$  IU/mL will undergo sequence analysis in order to allow accurate assessment of products of amplification. Therefore, if the HCV RNA level at the time of virologic failure or treatment discontinuation is  $< 1000$  IU/mL, the sample closest in time after failure/discontinuation with an HCV RNA level  $\geq 1000$  IU/mL will be used. Included time points for analyses on samples from subjects who do not achieve SVR12 are 1) the sample closest in time after failure/discontinuation

with an HCV RNA level of  $\geq 1000$  IU/mL, and 2) 24 weeks post-DAA treatment, provided that resistance-associated substitutions were detected at the time of failure/discontinuation.

The following definitions will be used in the resistance analyses by population sequencing:

- Baseline polymorphism: a polymorphism in a baseline sample determined by comparison of the amino acid sequence of the baseline sample to the appropriate prototypic reference amino acid sequence for a given DAA target.
- Post-baseline substitution: an amino acid substitution in a post-baseline time point sample that was not detected at baseline in the subject.

The following definitions will be used in the resistance analyses by NGS:

- Baseline polymorphism: a polymorphism in a baseline sample ( $\geq 2\%$  or  $\geq 15\%$  prevalence within a subject's viral population depending on frequency threshold utilized) that was not present in the appropriate prototypic reference amino acid sequence for a given DAA target (NS3/4A or NS5A).
- Substitution at signature amino acid position: substitution (relative to reference) present at a detection threshold of  $\geq 2\%$  or  $\geq 15\%$  (depending on frequency threshold utilized) within a subject's viral population in a baseline or a post-baseline sample at a signature amino acid position.
- Post-baseline substitution: an amino acid substitution in a post-baseline time point sample that was not detected at baseline ( $< 2\%$ ) in the subject and is detectable in  $\geq 2\%$  of the sequences from the sample.
- Enriched substitution: a substitution present at both baseline and in a post-baseline sample whose prevalence in the post-baseline sample is at least 20 percentage points greater than the prevalence in the baseline sample  $[(\text{post-baseline } \% - \text{baseline } \%) \geq 20]$ .
- Treatment-emergent substitution by NGS: a post-baseline substitution or an enriched substitution.

